11.4 Serious Adverse Events

If an AE is determined to be serious (i.e. an SAE), the Investigator(s) will determine the relationship of the adverse event to the procedure(s), device, or any commercial products used during the period of the study and complete an **Adverse Event Form**. Death is considered to be an outcome of an Adverse Event and documented on the Adverse Event Form. The actual cause of death (rather than the term “death”) should be recorded on the form. All SAEs will be followed until resolution or the Investigator judges the event to be chronic or stable.

11.5 Safety Reporting

All Adverse Events and Serious Adverse Events will be reported on an Adverse Event Form to the Sponsor as soon as possible after the Investigator first learns of the event. The Investigator must report all SAEs that meet the criteria below to a Zimmer Biomet Study Representative within twenty-four (24) hours after becoming aware of the incident:

- Definitely, probably or possibly related to the Study Procedure(s) and/or Study Implant AND unexpected

The Investigator is responsible for notifying their IRB/REB of all Adverse Events, including SAEs, in accordance with local regulations and institutional policies.

If an Unanticipated Serious Adverse Device Effect (USADE) is identified by the Sponsor, it will be promptly reported to concerned Investigators and regulatory authorities as required by applicable regulatory requirements. If applicable per their reporting requirements, the Investigator or Designee will report the USADE to their IRB/REB or EC.

Device deficiencies resulting in an adverse event will be documented on the Adverse Event form. Device deficiencies that could have led to a medical occurrence but did not lead to an adverse event will be reported to the sponsor within 48 hours of becoming aware of the event. The sponsor will process the device deficiency according to local complaint reporting procedures.

12.0 Assessment of Safety

All reports of Adverse Events will be entered into the study database and evaluated by the Sponsor on a regular basis throughout the study. These reports will be made available to the Investigator for preparation of IRB/REB continuing review reports, when requested.

Individual and aggregated events will be reviewed for consistency with expected events, for both severity and rate of incidence. Individual events or trends in events that appear to impact subject safety are reviewed by Zimmer Biomet management to determine if a change in the protocol or termination of the study is warranted. These decisions will be promptly communicated to all Investigators and local IRBs/REBs.

13.0 Compliance

13.1 Statement of Compliance

This clinical investigation will be conducted in accordance with the ethical principles that have their origin in the Declaration of Helsinki, Clinical investigation of medical devices for human subjects — ISO 14155:2020 Good Clinical Practice, and any regional or national regulations, as appropriate. The clinical investigation will not begin until all necessary approvals/favorable opinions are obtained from the appropriate IRB or REB or regulatory authority, as appropriate. Should an IRB or REB or regulatory authority impose any additional requirements, they will be followed. Information regarding the study and study data will be made available via publication on clinicaltrials.gov. Additionally, the results of this study will be offered for publication at the conclusion of the study, if participating investigators believe the data warrants publication in an appropriate journal.

13.2 Protocol Amendments

Any proposed amendments to this protocol must be submitted in writing, with a justification for the amendment, and approved by the Sponsor prior to implementation. All Sponsor-initiated protocol amendments will be documented in writing, including the date

and justification for the change, and communicated in a timely manner to the investigators. All amendments are to be approved by the reviewing IRB/REB prior to implementation, if required according to the local and/or national laws/regulations.

13.3 Monitoring Procedures

Prior to initiating the clinical study, the Sponsor may conduct a site evaluation visit to ensure the Investigator(s) and study staff understands the study protocol and requirements and have adequate time and resources to implement and conduct the study. Prior to study initiation, the Investigator must have a fully executed CTA and IRB or REB approval of the study protocol and the study Informed Consent.

During the course of the study, the Sponsor will conduct periodic central monitoring and maintain contact with the study staff to monitor compliance and evidence of adverse events, in accordance with the Sponsor's policies and procedures. The Sponsor will address any identified non-compliance with the executed CTA, study protocol, and applicable regulatory requirements.

If onsite monitoring visit(s) are deemed appropriate by the Sponsor, the Investigator will permit representatives of the Sponsor's monitoring team to have direct access to inspect all source data/documents, study documents/binders, study subject case report forms, corresponding sections of study subject medical/hospital records, and any other documents relevant to the study.

14.0 Statistical Considerations and Methodology

14.1 Primary Efficacy Endpoint Analysis

The primary measure of clinical success is a composite clinical success (CCS) endpoint requiring:

- Freedom from secondary subsequent surgical intervention (SSSI); and
- Among subjects free from SSSI; an improvement in KOOS pain of at least 10 points.

For the purpose of this study, SSSI will include any partial or total joint arthroplasty or any bone fixation, bone grafting or bone substitute procedure in the same compartment in the study knee.

14.2 Hypotheses

The primary hypotheses to be tested are symbolically represented as:

$$H_0: CCS(S+A) \leq CCS(AA) \text{ VS } H_a: CCS(S+A) > CCS(AA)$$

Where CCS(S+A) and CCS(AA) are equal to the probabilities of achieving composite clinical success for subjects undergoing Subchondroplasty with arthroscopy (S+A) compared to arthroscopy alone (AA). First, superiority will be statistically tested at 12 months using $\alpha=0.01$. If $p \leq 0.01$, then it will be concluded that S+A is superior to AA in terms of the primary endpoint and the conditional hypothesis of superiority in terms of ADL improvements will be tested, also at $\alpha=0.01$. If $p > 0.01$ at month 12, the same

hypothesis will be tested at month 24 using $\alpha=0.04$, thereby controlling the overall study type 1 error rate to no more than 0.05 according to the Bonferroni inequality. If $p \leq 0.04$ at month 24, it will be concluded that S+A is superior to AA in terms of the primary endpoint and the conditional hypothesis of superiority in terms of ADL improvements will then be tested at $\alpha=0.04$. The superiority hypotheses involving CCS will be tested using one-sided normal approximation tests. The conditional superiority test for improvements in ADL will be tested using one-sided contrasts derived from a mixed model for repeated measures (MMRM) for change in KOOS ADL among subjects free from SSSI.

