Materials and Methods	
Case report forms will be completed in-office or hospital at the Study Admit/Pre-Operative and Operative intervals. Subjects will be contacted via telephone for follow-up interviews at the 6 week, 3 month, 6 month, 9 month, 12 month, 18 month, and 24 month intervals. Post-Operative case report forms will be collected either by phone during these telephone interviews or by direct completion by the subject utilizing electronic patient reported outcomes (ePRO).

Statistical Considerations & Methodology	
The primary measure of clinical success is a composite clinical success (CCS) endpoint requiring:
 
 • Freedom from secondary subsequent surgical intervention (SSSI); and • Among subjects free from SSSI; an improvement in KOOS pain of at least 10 points. 
First, superiority will be statistically tested at 12 months using $\alpha=0.01$. If $p \leq 0.01$, then it will be concluded that S+A is superior to AA in terms of the primary endpoint and the conditional hypothesis of superiority in terms of ADL improvements will be tested, also at $\alpha=0.01$. If $p > 0.01$ at month 12, the same hypotheses will be tested at month 24 using $\alpha=0.04$, thereby controlling the overall study type 1 error rate to no more than 0.05 according to the Bonferroni inequality. If $p \leq 0.04$ at month 24, it will be concluded that S+A is superior to AA in terms of the primary endpoint and the conditional hypothesis of superiority in terms of ADL improvements will then be tested at $\alpha=0.04$. The conditional superiority test for improvements in ADL will be tested using one-sided contrasts derived from a mixed model for repeated measures (MMRM) for change in KOOS ADL among subjects free from SSSI.
 
A stratified blocked randomization will be used to assign subjects to either Subchondroplasty with arthroscopy or to arthroscopy

	
alone in a 2:1 ratio. Individual sets of blocks will be determined stratified by study site and lesion polarity status (unipolar vs bipolar).
 
Adverse events, serious adverse events, and surgical complications occurring from the time of surgery until the completion of the study will be recorded and tabulated by group. Summaries will consist of counts and percentages to describe the distribution of each safety endpoint.

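### Testing month 24 only when month 12 misses 0.01 is valid, but the condition is unnecessary and leaves the reserved 0.04 unused after a month-12 win

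*Combined protocol and SAP*

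**What the plan says.** Section 14.2 sets out two chains.

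- **Month 12.** "First, superiority will be statistically tested at 12 months using $\alpha=0.01". If CCS wins, "the conditional hypothesis of superiority in terms of ADL improvements will be tested, also at $\alpha=0.01". No further test is named on this branch.
- **Month 24.** This chain is entered on a condition, "If $p > 0.01$ at month 12, the same", and continues: "hypothesis will be tested at month 24 using $\alpha=0.04$, thereby controlling the overall study type 1 error rate to no more than 0.05". After a month-24 CCS win, the "conditional hypothesis of superiority in terms of ADL improvements will then be tested at $\alpha=0.04".

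The Synopsis (Section 3.0) gives the same rule: "If $p > 0.01$ at month 12, the same hypotheses will be tested at month 24 using $\alpha=0.04". The stated ground for error control is the Bonferroni inequality. Nowhere is the 0.04 carried forward after a month-12 win. Section 14.6 lists KOOS subscale changes and their course from 12 to 24 months as secondary endpoints, with no alpha assigned.

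**The concern.** A Bonferroni split pays for each test in advance. Once 0.01 and 0.04 have been set aside, both chains may be run whatever the other shows, so a condition linking them buys no error control.

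Here the condition has a price when the trial does well early. A month-12 CCS win closes the month-24 chain with its 0.04 unspent. The sponsor then has no alpha-controlled CCS result at 24 months, although subjects are followed that long. If ADL misses 0.01 at month 12, it cannot be tested at month 24, where 0.04 was available.

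**Working it through.** **Inputs from the documents.** CCS 0.80 vs 0.60; 116 and 58 evaluable; 80% power (Section 14.5). One-sided normal-approximation tests at 0.01 and 0.04 (Section 14.2).

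**Assumed, because the documents do not give them.** Equal CCS rates at both visits; between-visit correlation of the test statistics 0.5 to 0.7; CCS–ADL correlation 0.6; standardised ADL effects 0.3 to 0.5.

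**1. The plan's own figures.** The pooled rate is (2 × 0.80 + 0.60)/3 = 0.7333. With one-sided 0.04, power 0.80 and 2:1 allocation, the control-arm size is

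[1.751 × √(1.5 × 0.7333 × 0.2667) + 0.842 × √(0.24 + 0.16/2)]² / 0.2² = 50.7.

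The continuity correction raises this to 57.97, so 58, and 3 × 58 = 174, an exact match. None of the other variants tried gives 174 (for example one-sided 0.01: 228, or 249 with correction; one-sided 0.05: 141, or 162). The alpha total is 0.01 + 0.04 = 0.05, as stated.

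**2. Power at each visit, 116/58, without continuity correction.** The null standard error is √[0.7333 × 0.2667 × (1/116 + 1/58)] = 0.0711. The alternative standard error is √[0.16/116 + 0.24/58] = 0.0743.

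- Month 12 at 0.01: Φ[(0.20 − 2.326 × 0.0711)/0.0743] = Φ(0.465) = 0.679.
- Month 24 at 0.04: Φ[(0.20 − 1.751 × 0.0711)/0.0743] = Φ(1.016) = 0.845.

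Under the design scenario about two thirds of trials would take the branch on which the 0.04 is never used.

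**3. Chance of a formal month-24 CCS claim.** As written this is P(month 24 passes) − P(both pass). If always tested it is P(month 24 passes). The gain is therefore P(both pass), from a bivariate normal. The treatment rate is 0.80 throughout. Only the first row uses the design rates; the control rates and the 60/30 size in the other rows are illustrative.

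| Evaluable, control rate | Month-12 win | As written | Always tested | Gain |
|---|---|---|---|---|
| 116/58, 0.60 | 0.68 | 0.20–0.22 | 0.845 | 0.62–0.65 |
| 116/58, 0.70 | 0.21 | 0.23–0.25 | 0.39 | 0.14–0.17 |
| 116/58, 0.75 | 0.06 | 0.12–0.13 | 0.17 | 0.03–0.04 |
| 60/30, 0.70 | 0.11 | 0.17–0.19 | 0.25 | 0.06–0.08 |

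**4. At least one CCS win.** This is P(12 passes) + P(24 passes) − P(both pass) under either rule. In the design scenario it is 0.902 at correlation 0.5 and 0.879 at 0.7.

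**5. ADL claim at either visit.** Simulated with mean z = d × √(116 × 58/174) = 6.22d and the design CCS rates:

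| Effect d | As written | Always tested | Gain |
|---|---|---|---|
| 0.3 | 0.39–0.41 | 0.56–0.59 | 0.17–0.18 |
| 0.4 | 0.62–0.65 | 0.75–0.78 | 0.12–0.13 |
| 0.5 | 0.79–0.81 | 0.84–0.87 | 0.05–0.06 |

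**6. Error if both chains are always run.** ADL is tested only after CCS within each chain. In any null configuration the month-12 chain makes a false rejection with probability at most 0.01 and the month-24 chain at most 0.04; the sum is 0.05. A simulation of 2 million draws (correlations 0, 0.5 and 0.8; four effect configurations) gave 0.042 to 0.050. With month-12 CCS nearly certain to win, the current rule used only about 0.01.

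**The case against.** **A legitimate second-chance design.** Section 14.2 treats month 24 as a further test of one hypothesis, and the objective in Section 6.1 is superiority on CCS, not superiority at both visits. A month-12 win meets it. This stands: the rule is valid and, by step 4, costs no power for that objective. The documents do not explain the condition, though, and always testing keeps the second chance in full.

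**No 24-month durability claim is listed as an objective.** True, and month-24 KOOS results, including ADL, are still reported as secondary endpoints. A reader might infer that a month-12 win suppresses month-24 results. It does not; only the alpha-controlled claim is lost.

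**The design scenario has been overtaken.** Sections 3.0 and 7.0 say enrollment stopped after an interim analysis because control success was unexpectedly high. The change matters only after a month-12 win, which is now less likely. This stands, and it is why the lower rows of the table in step 3 matter more than the first.

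**The ADL figures are soft.** They assume all 116/58 are evaluable, whereas ADL is analysed only among subjects free from SSSI. Section 10.4.4 allows cross-over to Subchondroplasty, and Section 14.1 counts a bone substitute procedure in the same compartment as SSSI, so the month-24 set would be smaller and more selected. This stands.

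**A change after the interim analysis could look data-driven.** Section 14.3 itself cites the principle that the hierarchy be fixed in advance. On error control the objection fails. Every rejection under the current rule is also a rejection under the always-test rule, so whichever of the two is used, false rejections are confined to a set with probability at most 0.05. Disclosure is still needed.

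**Conclusion.** The condition is unnecessary, and removing it is a free improvement rather than a trade-off: no existing rejection is lost, each test keeps its alpha, and month-24 CCS and ADL tests are added.

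Two stronger readings are tempting. One is that the rule inflates type 1 error or weakens the primary comparison; steps 4 and 6 show that it does neither. The other is that this trial forfeits the full difference between 0.20–0.22 and 0.845. That difference belongs to the design scenario, and the documents give neither the achieved sample size nor the observed rates. After the early stop, gains of 0.03 to 0.17 (the three illustrative rows in step 3) are a fairer guide. All sizes assume equal rates at both visits and correlation 0.5 to 0.7; the ADL gain of about 0.05 to 0.18 also rests on the inputs questioned above. The point is low priority.

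**What to change.** In Section 14.2 and the Synopsis, remove the condition on the month-12 p-value and state:

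- Month-12 CCS is tested at 0.01 and, if significant, month-12 ADL at 0.01.
- Month-24 CCS is tested at 0.04 whatever the month-12 result and, if significant, month-24 ADL at 0.04.

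Make this a dated amendment before the final analysis, and say in the amendment and the final report that it follows the interim analysis. It needs no extra alpha, subjects or data. The cost is the amendment itself and the disclosure.

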7.0 Study Design

This is a multicenter, prospective, single-blinded, two-arm, randomized study. Enrolled subjects will have a single BML of the tibia, single BML of the femur, or adjoining BMLs of tibia and femur, as long as the BMLs are in the same compartment of the knee. Subjects will also be surgical candidates for knee arthroscopy due to mechanical symptoms, meniscus tear, loose body and/or synovitis.

A stratified blocked randomization will be used to assign subjects to either Subchondroplasty with arthroscopy or to arthroscopy alone in a 2:1 ratio. Individual sets of blocks will be determined within study site and lesion polarity status (unipolar vs bipolar).

Subjects will be consented within 90 days prior to surgery and take part in follow-up visits for two years following surgery. A preoperative visit (with exception of MR imaging) will occur within 60 days prior to surgery. Telephone follow-up interviews will be done at 6 weeks, 3 months, 6 months, 9 months, 18 months and 24 months post-surgery. Target enrollment is 201 subjects, to include 134 subjects in the treatment group (SCP + Arthroscopy) and 67 subjects in the control group (Arthroscopy alone).

Enrollment was stopped early when an interim analysis demonstrated that the study was unlikely to meet its primary endpoint due to an unexpectedly high success rate in the arthroscopy only group. Follow-up will continue for all subjects enrolled through the 24 month visit to allow further monitoring of outcomes related to revisions, reoperations, adverse events, and to collect KOOS assessments and numeric pain scores.

Subjects will complete the study at the 24 month follow-up visit. For the purposes of this protocol, a revision will be defined as any partial or total joint arthroplasty or any bone fixation, bone grafting or bone substitute procedure in the same compartment in the study knee.

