14.5 Sample Size Determination

For testing the primary superiority hypothesis as defined above and assuming true CCS rates of 0.80 and 0.60 for S+A and AA, respectively, a total of 174 subjects (116 and 58, respectively) are need for 80% power. This value is increased by 15% to 201 to account for losses-to-follow-up (134 S+A and 67 AA).

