14.10 Poolability, Stratified Analyses, and Covariates

Site poolability will be evaluated using a random effects meta-analysis approach using the R package metafor to implement the analysis. True effects are assumed to be normally distributed with mean μ and variance τ^2 .

By imposing a specified distribution on the site-to-site variability, i.e. a normal distribution with mean μ and variance τ^2 , sensitivity to small sample sizes in individual sites is reduced and the parameters reflecting the magnitude of site-to-site variability are naturally derived. The quantitative measure of the magnitude of heterogeneity is I^2 . I^2 is the fraction of τ^2 that is due to effect size heterogeneity, as opposed to sampling variance. Fractions 25% and less are considered small. If there is significant site to site variability, the impact on this variability will be evaluated using a random effects logistic regression.

Primary endpoints and selected secondary endpoints will be subjected to stratified analyses in order to evaluate poolability and heterogeneity of device group differences. Stratifications will include age (<55 vs ≥ 55 years), gender, body mass index (<30 vs ≥ 30 kg/m²), femoral vs tibial primary lesion, and unipolar vs bipolar lesion polarity status.

Analyses will focus on determining if clinically significant group differences exist for variables that potentially have important associations with clinical outcomes.

Identification of such variables will be based on clinical significance and not statistical significance since the study was not powered to detect any specific magnitude of difference between randomized groups. Nonetheless, conventional p-values for baseline group differences will be provided for descriptive purposes only and as a visual aid in identifying covariates worthy of further consideration. Variables for which clinically significant group differences are observed that are also associated with outcomes will be utilized as covariates in supporting analyses design to characterize how relative efficacy may vary

across subgroups. Additionally, using data from the investigational device only, a failure risk analysis will be performed starting with the same set of baseline covariates with the possible addition of procedure and device specific variables.

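### The primary CCS test is valid and meets its stated power, but it leaves out baseline KOOS pain and lesion polarity; prespecifying both is a cheap improvement with a gain that may be small

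*Combined protocol and SAP*

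**What the plan says.** - **Primary test (14.2).** "The superiority hypotheses involving CCS will be tested using one-sided normal approximation tests", at alpha 0.01 at month 12 and, if that fails, at 0.04 at month 24. No covariate or stratum is named.
- **Endpoint (14.1, 14.3).** Success needs freedom from SSSI and, among subjects free of it, a KOOS pain gain of at least 10 points on a 0–100 scale.
- **Randomisation (7.0).** "Individual sets of blocks will be determined within study site and lesion polarity status (unipolar vs bipolar"). The Synopsis allows up to 25 sites.
- **Sample size (14.5).** The plan is sized "assuming true CCS rates of 0.80 and 0.60 for S+A and AA, respectively". On those rates, the section concludes that "a total of 174 subjects (116 and 58, respectively) are need for 80% power".
- **Covariates (14.10).** "Variables for which clinically significant group differences are observed that are also associated with outcomes will be utilized as covariates in supporting analyses", whose purpose is to describe how relative efficacy varies across subgroups. The same section plans a random-effects look at sites, a random-effects logistic regression if site variability is significant, and analyses by subgroup, polarity included. None of these is the primary test, and baseline KOOS pain is not named as a covariate anywhere.
- **Status (7.0).** Enrolment stopped early after an interim analysis, because of high success in the arthroscopy-only group. The final number enrolled is not given.

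**The concern.** Baseline KOOS pain is part of the definition of the outcome. On a scale that ends at 100, a subject who starts above 90 cannot gain 10 points, and the entry rule (8.1, item 9) asks for one item rated at least moderate and sets no minimum subscale score. Baseline pain is collected before surgery (9.3, Table 1), so it can be used in the primary test at almost no cost. If it predicts CCS, the unadjusted test is less precise than it could be, in a trial that can no longer add subjects.

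There is also a prespecification issue. Under 14.10 the covariates depend on which imbalances happen to be seen and on their association with outcome, so the supporting estimate depends on the data. Naming the covariates in advance removes that.

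**Working it through.** **1. Reproduce the plan's sample size.** Inputs from 14.2 and 14.5: rates 0.80 and 0.60, 2:1 allocation, one-sided alpha 0.04, power 0.80.

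- Mean rate = (0.60 + 2 × 0.80)/3 = 0.7333; 0.7333 × 0.2667 = 0.1956.
- AA subjects, no continuity correction: n = [1.751 × √(1.5 × 0.1956) + 0.842 × √(0.24 + 0.16/2)]² / 0.20² = 50.7, so 51 and a total of 153.
- With continuity correction: (50.7/4) × [1 + √(1 + 3/(50.7 × 0.20))]² = 57.97, so 58 AA, 116 S+A and **174** in total, an exact match.

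The sizing therefore rests on an unadjusted two-proportion test at the month-24 alpha, and it delivers its 80%.

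**2. Power with adjustment, by formula.** Treat adjustment as raising the effective AA sample to n = 58/(1 − R²), and compute

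power = Φ[(0.20 − z × √(0.1956 × 1.5/n)) / √(0.32/n)], with z = 1.751 (alpha 0.04) or 2.326 (alpha 0.01), no continuity correction.

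Worked case, R² = 0.10, alpha 0.04: n = 64.4; (0.20 − 1.751 × 0.0675)/0.0705 = 1.16; Φ = 0.877.

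| R² (assumed) | alpha 0.04 | alpha 0.01 |
|---|---|---|
| 0 (unadjusted) | 84.5% | 67.9% |
| 0.01 | 84.9% | 68.4% |
| 0.02 | 85.2% | 68.9% |
| 0.05 | 86.1% | 70.4% |
| 0.10 | 87.7% | 72.9% |
| 0.15 | 89.3% | 75.6% |
| 0.20 | 90.9% | 78.3% |

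Equivalently, the 153 needed without continuity correction becomes 153 × (1 − R²): 145 at R² 0.05, 138 at 0.10, 122 at 0.20.

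**3. Plausible R², and whether the choice of test matters.** CCS was simulated at 116/58 from baseline and follow-up KOOS pain, 4,000 trials per scenario. Assumed, not from the documents: baseline SD 15, follow-up SD 15 or 20, correlation 0.3 to 0.7. Power at alpha 0.04:

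| Correlation, follow-up SD | R² | Unadjusted z | Logistic score test | Standardised risk difference (Wald) |
|---|---|---|---|---|
| 0.3, 15 | 0.20 | 85.2% | 91.7% | 91.0% |
| 0.5, 15 | 0.147 | 84.9% | 90.0% | 88.7% |
| 0.3, 20 | 0.11 | 84.0% | 87.3% | 86.3% |
| 0.7, 15 | 0.094 | 85.2% | 87.6% | 86.0% |
| 0.5, 20 | 0.054 | 85.5% | 87.2% | 85.9% |
| 0.7, 20 | 0.016 | 85.6% | 85.5% | 83.6% |

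The score test gains from nil to 6.5 points and never materially loses. The Wald test of the standardised risk difference loses 2 points in the last row, and about 4 at alpha 0.01 (68.9% to 65.1%). Simulated type I error was close to nominal for every method, the unadjusted test included.

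**4. The randomisation strata.** Up to 25 sites × 2 polarity levels = 50 cells. Even at the planned 201 subjects that is 201/50 = 4.0 subjects and 67/50 = 1.3 controls per cell. With 20 sites assumed (40 cells), a Mantel–Haenszel test on site by polarity had simulated power of 81.5–84.0% against 84.3–85.4% unadjusted at alpha 0.04, a loss of about 1 to 3 points. Stratifying on polarity alone, when it is not prognostic, changed power by no more than about half a point.

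**The case against.** The strongest case for leaving 14.2 alone is that nothing is broken: the unadjusted test holds its error rate, the sample size reproduces, and the plan meets its own power target. That stands, and it makes this a matter of efficiency and prespecification.

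Three stronger readings are tempting, and the documents support none of them.

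- *Analysing by the randomisation factors gives power for free.* Nothing in the documents shows that site or polarity predicts CCS, and stratifying on every cell costs power (step 4). The likely source of gain is baseline pain.
- *A gain of a few points is assured.* It rests on an R² the documents do not give and on the form of test; at the low end it is nil.
- *Adjustment would have rescued the trial.* The stated reason for stopping was a high control success rate. A modest gain in precision does not replace a difference smaller than 0.20, and every power above is at the design numbers, not at the unreported final number.

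An interim analysis has also been seen, so replacing the primary test now can look data-driven. That objection has weight: it does not rule the change out, but it calls for a dated rationale and makes a named supporting analysis a reasonable alternative. Finally, 14.10 is milder than it may appear. Its covariates serve supporting analyses only, and its baseline p-values are described as descriptive.

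**Conclusion.** The point holds as a cheap improvement. The primary CCS test is valid and adequately powered on the plan's own assumptions, but it uses neither baseline KOOS pain nor polarity, and 14.10 does not fill the gap. Adjusting for baseline pain is worth between almost nothing and about 6 points of power at alpha 0.04, and between almost nothing and about 10 points at alpha 0.01. These figures assume R² of about 0.01 to 0.20, 116/58 evaluable subjects and true rates of 0.80 and 0.60. The size of the gain in this trial cannot be known from the documents.

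**What to change.** Before data lock (17.3):

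1. In 14.2, make the primary test a one-sided logistic score test of arm, adjusted for baseline KOOS pain and for polarity as entered at randomisation, at 0.01 (month 12) and 0.04 (month 24). Fixing polarity at randomisation matters because 14.8 finalises stratum assignment during surgery.
2. Report the standardised risk difference with a robust standard error as the estimate, and state that the score test decides.
3. Do not stratify on the full site-by-polarity cells. State in advance whether small sites are pooled or site is omitted.
4. Keep the unadjusted z test as a sensitivity analysis.
5. Use the same test for the tipping-point p-values in 14.9. An adjusted p-value depends on which missing subjects are counted as successes as well as how many, so a rule for assigning them is needed.
6. In 14.10, replace the imbalance-driven choice of covariates with these named ones.

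The cost is SAP wording and slightly more analysis work. Because an interim analysis has been seen, record the date of the change and its rationale. If the sponsor will not alter the primary test for that reason, make this model the single named supporting analysis.

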14.6 Analysis of Secondary Endpoints

The following secondary endpoints will be examined:

- 1) Comparison of mean change in KOOS Pain, ADL, Symptoms, Sports and Recreation, Quality of Life Subscale scores
- 2) Longitudinal comparison of KOOS subscales over 12 to 24 months post-surgery
- 3) Comparison of mean Numeric Pain, EQ-5D and Global Satisfaction scores, where available
- 4) X-ray evaluation of joint space narrowing, osteophyte and cyst formation and subchondral sclerosis, where available
- 5) MRI analysis of bone marrow lesion variables, where available
- 6) Incidence and time to resolution of post-operative complications and adverse events
- 7) Incidence and time to joint injections, where available
- 8) Incidence and time to re-operations and revisions
- 9) Number of visits to healthcare providers, diagnostic or treatment procedures, and support devices; use of pain medication; and days of productivity lost, where available.

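### The plan does not commit to baseline score or lesion polarity as model terms for KOOS ADL, the KOOS subscales or Numeric Pain, and read naturally it gives up precision

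*Combined protocol and SAP*

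**What the plan says.** The conditional ADL test (14.2, repeated in the synopsis) is to use "one-sided contrasts derived from a mixed model for repeated measures (MMRM) for change in KOOS ADL among subjects free from SSSI". No fixed effects, covariates or covariance structure are listed. It is run only if CCS is significant, at one-sided 0.01 at month 12 or 0.04 at month 24.

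Section 14.6 is a list of endpoints. For the five KOOS subscales it names a comparison of mean change. For the pain scale it reads "Comparison of mean Numeric Pain, EQ-5D and Global Satisfaction scores, where available", with no mention of change, baseline or model.

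Section 14.10 holds the only covariate rule. Baseline variables on which the groups are seen to differ to a clinically significant degree, and which are also associated with outcome, "will be utilized as covariates in supporting analyses design to characterize how relative efficacy may vary" across subgroups. Lesion polarity appears there only as a factor for stratified analyses of the primary and selected secondary endpoints.

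The inputs for adjustment exist. KOOS and Numeric Pain are completed before surgery (Section 9.3 and Table 1). On randomisation, Section 7.0 states: "Individual sets of blocks will be determined within study site and lesion polarity status (unipolar vs bipolar").

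**The concern.** For a continuous outcome with a measured baseline, a comparison of change subtracts the whole baseline, which over-corrects whenever the correlation with follow-up is imperfect. A comparison of follow-up means ignores the baseline. Putting the baseline in the model as a covariate uses it with the right weight. It also removes the part of a chance baseline difference that would otherwise move the estimate. A factor used to stratify randomisation would normally be in the model too.

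No section makes either term part of the planned analysis. ADL is the only claim besides CCS that sits inside the alpha-controlled sequence. The KOOS subscales and Numeric Pain lie outside it. They are, however, the outcomes for which Section 7.0 keeps subjects in follow-up after enrolment stopped, and they will come from fewer subjects than planned.

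**Working it through.** **The plan's own figure.** Section 14.5 sizes the trial for CCS only: rates 0.80 and 0.60, 2:1 allocation, 80% power, 116 + 58 = 174. With one-sided alpha 0.04 (z = 1.751), power z = 0.842 and pooled rate (0.60 + 2 × 0.80)/3 = 0.733:

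- n(AA) = [1.751 × √(1.5 × 0.733 × 0.267) + 0.842 × √(0.24 + 0.16/2)]² / 0.20² = 50.7.
- The continuity correction raises this to 58, so the total is 58 + 116 = 174, an exact match.
- 174 × 1.15 = 200.1, or 201 in whole 2:1 sets.

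Neither ADL nor Numeric Pain enters this calculation. The plan states no power for them.

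**Variance of the treatment contrast.** Assume equal SD at baseline and follow-up and correlation rho between them. Both are assumptions; the documents give neither. Relative to the follow-up variance:

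- unadjusted change: 2(1 − rho)
- raw follow-up mean: 1
- baseline as covariate: 1 − rho²

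Adjusted over change is therefore (1 − rho²)/[2(1 − rho)] = (1 + rho)/2. Adjusted over raw mean is 1 − rho².

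| rho (assumed) | adjusted / change | variance cut | adjusted / raw mean | variance cut |
|---|---|---|---|---|
| 0.3 | 0.65 | 35% | 0.91 | 9% |
| 0.5 | 0.75 | 25% | 0.75 | 25% |
| 0.7 | 0.85 | 15% | 0.51 | 49% |

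A simulation with arms of 116 and 58 gave ratios of 0.66, 0.77, 0.86 and 0.91, 0.75, 0.51, in agreement. In subjects, the precision of 174 analysed on unadjusted change would need about 174 × 0.65 = 113, 174 × 0.75 = 131 or 174 × 0.85 = 148 with adjustment.

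**High correlation.** The only reliability figures in the documents are the 2-day test-retest ICCs of 0.87 to 0.95 (14.3). Used as a rough ceiling for rho, they give ratios of (1 + 0.87)/2 = 0.935 and (1 + 0.95)/2 = 0.975, a saving of 6.5% to 2.5% for change scores.

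**Unequal SDs.** The variance saved against change is (SD_baseline − rho × SD_follow-up)². It can be small but is never negative, apart from the degrees of freedom used.

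**ADL power, illustration only.** Suppose the unadjusted change test had 80% power. Adjusted power is Φ[(z_alpha + 0.842)/√ratio − z_alpha], with z_alpha = 2.326 at 0.01 and 1.751 at 0.04.

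| rho | alpha 0.01 | alpha 0.04 |
|---|---|---|
| 0.3 | 95% | 93% |
| 0.5 | 91% | 89% |
| 0.7 | 87% | 86% |
| 0.87 to 0.95 | 83% to 81% | 82% to 81% |

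**Polarity.** Its prevalence and its association with outcome are not given, so no gain can be computed.

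**The case against.** The strongest reply is that the plan is silent rather than wrong. An MMRM on change can contain baseline, and 14.2 does not even list treatment or visit. Section 14.6 names no model for Numeric Pain. Section 14.10 does not say that covariates may enter only supporting analyses, and it already provides an imbalance review and analyses by polarity. This stands as far as wording goes. A reader might infer that the plan prescribes unadjusted models; the documents do not say so. They fail to commit to these terms, and the one rule they give points the other way.

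A reader might also infer bias or a false-positive risk. Under randomisation, omitting baseline does not bias the contrast, and omitting a stratification factor from a linear model tends to make the test conservative.

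The size rests on assumptions: rho, equal SDs, the 80% starting power, and a single-visit formula standing in for an MMRM. The planned arms of 116 and 58 are not those that will be analysed. The ADL test may never run, because the protocol itself says the primary endpoint is unlikely to be met. All of this stands and limits the weight of the point.

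Site is the other stratification factor and is not proposed here. With up to 25 sites, fixed site effects could use up to 24 degrees of freedom, and 14.10 already examines site variability with a random-effects approach.

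**Conclusion.** The point holds as a loss of efficiency. No section commits to baseline score or polarity in the ADL, KOOS subscale or Numeric Pain analyses, although both are available. On the natural, unadjusted reading, baseline adjustment would cut variance by 15% to 35% for change scores and by 9% to 49% for raw Numeric Pain means, over an assumed rho of 0.3 to 0.7 with equal SDs. At a rho near the 2-day ICCs, the change-score gain shrinks to 2.5% to 6.5%. The direction does not depend on the assumptions; the size does. Including polarity rests on analysing as randomised, not on a computed gain. The CCS test is not affected. Because ADL is tested only after CCS succeeds, the main practical benefit is to the KOOS subscale and Numeric Pain results, in a sample smaller than planned.

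**What to change.** Before data lock (17.3):

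- In 14.2 and the synopsis, state that the ADL MMRM includes treatment, visit, treatment-by-visit, baseline KOOS ADL, baseline-by-visit and lesion polarity as randomised, with the contrast taken at month 12 or month 24.
- In 14.6, apply the same model to each KOOS subscale and to Numeric Pain, each with its own baseline and the visits at which it is collected (at 9 months, KOOS Pain only).
- In 14.10, state that the supporting-analysis rule does not govern these pre-specified terms.

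The cost is wording and a few model degrees of freedom; no new data are needed. Since an interim analysis has already taken place, the amendment should record that the terms were fixed after it, and were chosen only from each measure's baseline and the stratification factor.
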